The original development plan (at the time of the ongoing Ebola epidemic in Africa) was an accelerated plan with the anticipation of conducting Phase 3 efficacy studies (with limited safety data collection) shortly after Phase 1 and in parallel with Phase 2. The sponsor designed the VAC52150EBL4001 study for the extended follow-up of serious adverse events (SAEs) to enhance the ability for signal detection of rare events. Since there is no longer an ongoing Ebola epidemic, it is not currently possible to conduct a parallel Phase 3 efficacy study as part of an accelerated development plan. More controlled safety data will become available for all vaccinated subjects, therefore, prior to any potential future efficacy study.

The changes made to the clinical protocol VAC52150EBL4001 are listed below, including the rationale of each change and a list of all applicable sections.

Rationale: It was specified that each local authority will determine which cohorts will be opened for enrollment in their region. It is not mandatory to open all cohorts for enrollment. As a result, a local authority may restrict enrollment to 1 or 2 cohorts, rather than allowing enrollment in all cohorts. The approximate number of subjects potentially to be enrolled in this study was updated.

SYNOPSIS

- 3.1 Overview of Study Design
- **5 SUBJECT POPULATION**
- 5.1 Inclusion Criteria
- 11.2 Sample Size Determination

Rationale: Updates were made to the Background section and references were added to the latest versions of the Investigator's Brochure of Ad26.ZEBOV and MVA-BN-Filo. In addition, the potential risk of myo/pericarditis was removed because no cardiovascular events were associated with the current MVA-BN-Filo vaccine.

- 1.1 Background
- 1.2 Benefit/Risk Section
- 1.2.4 Potential Risks

REFERENCES

Rationale: Minor editorial changes have been made throughout the document.

- 1.1 Background
- 5.1 Inclusion Criteria

4

Amendment 1 (30 September 2016)

This amendment is considered to be substantial based on the criteria set forth in Article 10(a) of Directive 2001/20/EC of the European Parliament and the Council of the European Union.

The overall reason for the amendment: Since validated assays are not available yet to assess immune responses in the ongoing Phase 2 and 3 studies, unblinding of these studies has been delayed. Therefore, subjects who received placebo in their original Phase 2 or 3 study will also be approached for enrollment into the VAC52150 Vaccine Development Roll-over study before unblinding of their original study.

The changes made to the clinical protocol VAC52150EBL4001 are listed below, including the rationale of each change and a list of all applicable sections.

Rationale: Unblinding of the ongoing Phase 2 and 3 studies has been delayed. Therefore, placebo subjects from these studies who reach the last study visit before unblinding of their original study, will be approached for enrollment into the VAC52150 roll-over study. Details on the procedures for these subjects have been added.

SYNOPSIS

Time and Events Schedule

- 3.1 Overview of Study Design
- 4 TREATMENT ALLOCATION AND BLINDING
- **5 SUBJECT POPULATION**
- 8 Medication and Vaccinations
- 9.1 Study Procedures
- 9.2.1 Exposure Definition
- 9.2.2 Evaluations
- 10.1 Completion
- 10.2 Withdrawal From the Study
- 11.2 Sample Size Determination
- 11.4 Subject Information
- 11.5 Safety Analyses
- 12.3.2 Pregnancy

Rationale: Safety information following MVA-BN-Filo vaccine administration based on the pooled safety data from studies VAC52150EBL1001 and VAC52150EBL1002 has been included.

- 1.1 Background
- 1.2.3 Known Risks
- 1.2.4 Potential Risks

Rationale: Based on the request of the Food and Drug Administration, the study phase is updated to Phase 3.

Title Page

Rationale: Name change from Crucell Holland B.V. to Janssen Vaccines & Prevention B.V.

Title Page

1 INTRODUCTION

REFERENCES

INVESTIGATOR AGREEMENT

Rationale: Minor textual changes have been made, in addition to modifications for clarity and updates to be in line with other current protocols and the current Investigator Brochures.

SYNOPSIS

1 INTRODUCTION

5 SUBJECT POPULATION

SYNOPSIS

A Multi-country, Prospective, Clinical Safety Study of Subjects Exposed to the Candidate Ebola Vaccines Ad26.ZEBOV and/or MVA-BN-Filo

The sponsor, in collaboration with Bavarian Nordic GmbH (BN), is investigating the potential of a prophylactic Ebola vaccine regimen comprised of the following 2 candidate Ebola vaccines:

Ad26.ZEBOV is a monovalent vaccine expressing the full length Mayinga glycoprotein (GP) of the Ebola virus (EBOV, formerly known as *Zaire ebolavirus*), and is produced in the human cell line PER.C6®.

MVA-mBN226B, further referred to as Modified Vaccinia Ankara (MVA)-BN®-Filo, is a multivalent vaccine expressing the Sudan virus (SUDV) GP, the EBOV GP, the Marburg virus (MARV) Musoke GP, and the Tai Forest virus (TAFV, formerly known as *Côte d'Ivoire ebolavirus*) nucleoprotein (NP), and is manufactured in chicken embryo fibroblast cells. The EBOV GP expressed by MVA-BN-Filo has 100% homology to the one expressed by Ad26.ZEBOV.

The EBOV GP that circulated in West Africa has 97% homology to the EBOV GP used in these vaccine regimens.

Ad26.ZEBOV and MVA-BN-Filo are being evaluated in Phase 1, 2 and 3 clinical studies, in different heterologous prime-boost regimens, in which one study vaccine is used to prime a filovirus-specific immune response and the other study vaccine is used to boost the immune response. Homologous regimens for each vaccine are also being evaluated.

OBJECTIVES AND HYPOTHESIS

Objectives

The study objectives are:

- To collect serious adverse event information from subjects exposed to Ad26.ZEBOV and/or MVA-BN-Filo in a Phase 1, 2, or 3 clinical study, for a total of 60 months after prime vaccination (including the duration in the subject's original study).
- To collect pregnancy outcomes (including spontaneous/elective abortion, intrauterine death/stillbirth, information on delivery) and serious adverse event information during pregnancy from female subjects who became pregnant with estimated conception within 28 days after vaccination with MVA-BN-Filo or within 3 months after vaccination with Ad26.ZEBOV in a Phase 1, 2 or 3 clinical study.
- To collect serious adverse event information for up to 60 months after birth from children born to female subjects who became pregnant with estimated conception within 28 days after vaccination with MVA-BN-Filo or within 3 months after vaccination with Ad26.ZEBOV in a Phase 1, 2 or 3 clinical study.

Hypothesis

This is a descriptive study to document the long-term safety profile of Ad26.ZEBOV and MVA-BN-Filo and to address gaps in the currently available data for the risks of Ad26.ZEBOV and/or MVA-BN-Filo. As this study aims to describe the data for benefit-risk assessment purposes, no hypotheses are prespecified.

OVERVIEW OF STUDY DESIGN

This is a multi-country, prospective, long-term clinical safety study designed to extend the total follow-up period of vaccinated subjects up to 60 months (including the duration in the subject's original study), to allow collection of serious adverse events and pregnancy outcomes (including spontaneous/elective abortion, intrauterine death/stillbirth, information on delivery) following administration of Ad26.ZEBOV and/or MVA-BN-Filo for the prevention of Ebola virus disease among subjects who participated in a Phase 1, 2 or 3 clinical study. In addition, offspring from vaccinated female subjects who became pregnant with estimated conception within 28 days after vaccination with MVA-BN-Filo or within 3 months after vaccination with Ad26.ZEBOV in a Phase 1, 2 or 3 clinical study will be followed up to 60 months after birth. Up to approximately 3,000 subjects may potentially be enrolled in this study, based on the number of exposed subjects in the contributing Phase 1, 2 or 3 clinical studies.

Since validated assays are not available yet to assess immune responses in the ongoing Phase 2 and 3 studies, unblinding of these studies has been delayed. Therefore, subjects in the ongoing Phase 2 and 3 studies who reach the last study visit will be approached to consent for enrollment into the VAC52150 Vaccine Development Roll-over study for long-term safety surveillance (for a total of up to 60 months after the prime vaccination). After unblinding of their original study only subjects who received Ad26.ZEBOV and/or MVA-BN-Filo will remain in this VAC52150 Vaccine Development Roll-over study for long-term safety surveillance. After unblinding, subjects who received placebo and have already been enrolled into the VAC52150 Vaccine Development Roll-over study will be discontinued from further participation in this roll-over study. This also applies to pregnant subjects who received placebo (ie, subjects enrolled in Cohort 2) or offspring from vaccinated female subjects who received placebo (ie, subjects enrolled in Cohort 3).

The study will consist of an enrollment visit, a number of follow-up contacts and an end-of-study contact. These contacts are preferably conducted by phone; if not possible, a study site visit needs to be organized. Preferably, offspring from vaccinated female subjects will visit the study site for every study visit. If not possible, the child may be visited at home by study site staff or a qualified health care worker for data collection.

Data collection can start when a signed informed consent form (ICF) is available for the current study. Preferably, signing of the ICF occurs at the last visit of the subject's original study (or at birth for offspring). If this is not possible, baseline data will be collected when a signed ICF is available and data need to be captured retrospectively up to the moment of enrollment in the current study.

Data collection will be as follows for the 3 cohorts:

Cohort 1: Data for subjects vaccinated with Ad26.ZEBOV and/or MVA-BN-Filo (or placebo) in a Phase 1, 2 or 3 clinical study (adults, adolescents and children) and who consent to participation in the current study will be collected in 6-month intervals. Data collection will continue for a total of 60 months after prime vaccination (including the duration in the subject's original study).

Cohort 2: Data on the pregnancy outcome of female subjects who became pregnant with estimated conception within 28 days after vaccination with MVA-BN-Filo (or placebo) or within 3 months after vaccination with Ad26.ZEBOV (or placebo) in a Phase 1, 2 or 3 clinical study and who consent to participation in the current study will be collected at notification of the pregnancy, and at the end of the pregnancy. These subjects will be followed in Cohort 2 up to the end of their pregnancy. Thereafter, female subjects will continue to be followed in Cohort 1 (to reach a total of 60 months follow-up after prime vaccination including the duration in the subject's original study); live-born children will be followed in Cohort 3.

Cohort 3: Data for children born to female subjects exposed to Ad26.ZEBOV and/or MVA-BN-Filo (or placebo) in a Phase 1, 2 or 3 clinical study who became pregnant with estimated conception within 28 days after vaccination with MVA-BN-Filo (or placebo) or within 3 months after vaccination with

Ad26.ZEBOV (or placebo) and for whom consent for the current study is given, will be collected in 6-month intervals, and up to 60 months after birth.

Each local authority will determine which cohorts will be opened for enrollment in their region. It is not mandatory to open all cohorts for enrollment. As a result, a local authority may restrict enrollment to 1 or 2 cohorts, rather than allowing enrollment in all cohorts.

After unblinding of their original study, subjects from Cohort 1 and 2 who received placebo or offspring (Cohort 3) from female subjects who received placebo will be discontinued from further participation in this roll-over study.

SUBJECT POPULATION

The study will be open to subjects who participated in a Phase 1, 2 or 3 clinical study with Ad26.ZEBOV and/or MVA-BN-Filo and who received at least one dose of study vaccine (active vaccine or placebo).

SAFETY EVALUATIONS

Serious adverse event information in each cohort, pregnancy outcomes (including spontaneous/elective abortion, intrauterine death/stillbirth, information on delivery) and growth measurements for offspring will be collected.

STATISTICAL METHODS

There are no planned interim analyses. However, the accumulating data during study conduct may be used for reporting required for health authority submissions or other purposes. As this is a non-comparative study without formal hypotheses, any interim data may be used for purely administrative purposes without having an impact on study conduct or need for statistical adjustments. All interim reporting must be approved by the study responsible physician and project statistician prior to conduct.

No formal statistical testing of safety data is planned. Incidence rates of serious adverse events in each cohort, of pregnancy overall and by pregnancy outcome (including spontaneous/elective abortion, intrauterine death/stillbirth, information on delivery) will be calculated for all events and the number of events per person-year (where applicable), with corresponding 2-sided 95% confidence intervals. Incidence rates will also be tabulated by age group.

Results for subjects who received active vaccine or placebo will be presented separately.

TIME AND EVENTS SCHEDULE

1. COHORT 1: VACCINATED SUBJECTS

Data collection schedule for subjects exposed to Ad26.ZEBOV and/or MVA-BN-Filo (or placebo) in a Phase 1, 2 or 3 clinical study:

	Visit 1 ^a	Contact 2 ^a	Subsequent Contacts ^a	End of Study ^a
	Baseline (Start of Data Collection) ^b	Month 6	Every 6 Months	After 60 Months of Follow-up ^c
Subject information				
Subject consent ^d	X			
Selection criteria	X			
Demographics ^e	X			
Ongoing subject review				
Serious adverse events ^{e,f}	X	X	X	X
Medication and vaccinations ^{e,g}	X	X	X	X
Study completion/withdrawal				
End-of-study form				$X^{\mathbf{h}}$

- a. Only the first visit is a study site visit (and may coincide with the last visit in the subject's original study); data collection at other time points will preferably occur through phone calls. If not possible by phone, a study site visit needs to be organized.
- b. Data collection can start when a signed informed consent form (ICF) is available for the current study. Preferably, this occurs at the last visit of the subject's original study. If this is not possible, baseline data will be collected when a signed ICF is available and data will be captured retrospectively from the subject's last visit in the original study up to the moment of enrollment in the current study.
- c. The subject should be followed for a total of 60 months after prime vaccination, including the duration in the subject's original study.
- d. Before the start of data collection in this study, all subjects and/or their legally-acceptable representative (where applicable) must sign an ICF for the current study indicating that he or she understands the purpose of and procedures required for the study and is willing to participate in the study.
- e. Relevant data will be copied from the analysis data set of the subject's original study. Any relevant new information should be added in the Case Report Form (CRF) of the current study.
- f. All serious adverse events are to be documented for a total of 60 months after prime vaccination (including the duration in the subject's original study).
- g. Any medication taken within a period of 30 days prior to the onset of a serious adverse event and up to the resolution of the serious adverse event.
- h. When an enrolled subject completes or withdraws from the study, or is lost to follow-up, the investigator will complete the end-of-study form for the individual subject and provide a specific date for the end-of-study observation(s).

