3.2. Study Design Rationale

The prospective design of the study was chosen to specifically meet the study objectives. Prospective data collection facilitates active pharmacovigilance via real-time identification and reporting of serious adverse events and facilitates collection of a sufficient quantity of defined variables to address the study objectives of characterizing serious adverse events and pregnancy outcomes. The study design was chosen to observe long-term safety outcomes following Phase 1, 2 and 3 clinical studies.

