9. STUDY EVALUATIONS

9.1. Study Procedures

The Time and Events Schedule summarizes the frequency and timing of data collection in this study. The documentation of data must be performed according to Good Clinical Practice (GCP) and professional guidelines.

Prior to data collection, all subjects or their parent/legally acceptable representative (where applicable) must sign an ICF for the current study indicating that he or she understands the purpose of and procedures required for the study and is willing to participate in the study or let their child participate. Preferably, consent will be obtained at the last visit of the subject's original study or at birth for offspring. If this is not possible, the consent can be given at a later time point, allowing collection of baseline data to be conducted retrospectively up to the moment of enrollment in the current study. Relevant data should be copied from the analysis data set of the subject's original study. Any relevant new information should be added to the CRF of the current study.

Where available (and applicable to the cohort), the following items are to be documented or captured from the original analysis data set at baseline and/or during the long-term follow-up period:

- Demographic data (at baseline only);
- Serious adverse events
- Any medication taken within a period of 30 days prior to the onset of a serious adverse event and up to the resolution of serious adverse event;
- Vaccinations (including routine vaccinations for children);
- Pregnancy follow-up, including information on obstetric history, maternal/paternal risk factors, pregnancy outcome (including spontaneous/elective abortion, intrauterine death/stillbirth, information on delivery);
- Follow-up of offspring, including information on birth (preterm/full term), growth measurements at birth and subsequent visits (height and weight, including growth percentiles), presence of birth defects, medical interventions beyond routine interventions at birth. Medical history of the child may include relevant information from the mother's pregnancy follow-up, family history of growth (details on stature of parents and siblings).

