9.2.2. Evaluations

Serious Adverse Events

For the prospective study period, all serious adverse events, related or not related, following exposure of subjects to Ad26.ZEBOV and/or MVA-BN-Filo (or placebo) or in offspring are to be recorded in the CRF and in the subject's source documents.

Section 12 provides further details of safety reporting procedures.

Any serious adverse events persisting at the end of the study/early withdrawal will be followed by the investigator until resolution or until a clinically stable endpoint is reached.

Pregnancy Outcomes

For the prospective study period, all pregnancy outcomes (including spontaneous/elective abortion, intrauterine death/stillbirth, information on delivery) following pregnancy of a female subject who became pregnant with estimated conception within 28 days after vaccination with MVA-BN-Filo (or placebo) or within 3 months after vaccination with Ad26.ZEBOV (or placebo) are to be recorded in the CRF and in the subject's source documents.

Growth Measurements

For the prospective study period, growth measurements for offspring (including height, weight and growth percentiles) are to be recorded in the CRF and in the subject's source documents.

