10.2. Withdrawal From the Study

A subject may be withdrawn from data collection in this study for any of the following reasons:

- Withdrawal of consent
- Lost to follow-up
- Death

After unblinding of their original study, subjects who received placebo will be withdrawn from further participation. This also applies to pregnant subjects who received placebo (ie, subjects enrolled in Cohort 2) or offspring from vaccinated female subjects who received placebo (ie, subjects enrolled in Cohort 3).

Subjects who are subsequently enrolled as a subject in another non-sponsor clinical study do not need to be withdrawn from the study. It is accepted that data collection in this study may be restricted by confidentiality agreement terms and/or conditions of another concurrent clinical study.

When a subject withdraws before completing the study, the reason for withdrawal is to be documented in the CRF and in the source documents.

If a subject is lost to follow-up, every reasonable effort must be made by the study-site personnel to contact the subject and determine the reason for withdrawal. The measures taken to follow up must be documented. In the event that the status of the subject cannot be determined and the

subject is considered to be lost to follow-up, an end-of-study form for the individual subject will be completed and a specific date for the last observation will be provided.

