11.5. Safety Analyses

The verbatim terms used in the CRF by investigators to document serious adverse events will be coded using the Medical Dictionary for Regulatory Activities (MedDRA). All serious adverse events will be included in the analysis. For each serious adverse event, the percentage of subjects who experience at least 1 occurrence of the given event and the number of events per person-year (where applicable) with corresponding 2-sided 95% confidence intervals will be provided, for each cohort and by original randomization (active vaccine versus placebo). In addition, these analyses will be provided by age group for Cohort 1.

The incidence of pregnancy, incidence of pregnancy outcomes (including spontaneous/elective abortion, intrauterine death/stillbirth, information on delivery) and incidence of live-born children will be summarized by original randomization (active vaccine versus placebo). Only pregnancies with estimated conception within 28 days after vaccination with MVA-BN-Filo or within 3 months after vaccination with Ad26.ZEBOV, and live-born children from these pregnancies, will be included.

Results for subjects who received active vaccine or placebo will be presented separately.

A summary for subjects who die or who discontinue due to a serious adverse event will be provided.

The use of medications taken in relation to serious adverse events will be summarized.

Additional summaries, listings, datasets, or subject narratives may be provided, as appropriate.

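### Cohort 1 time before a late roll-over consent is captured retrospectively, without limit, and is not separated from prospective follow-up in the 60-month SAE rate, so the absolute vaccine rate can be biased low

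*Protocol*

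**What the plan says.** Consent at the last original-study visit is the preferred route. Where that fails, Section 9.1 says "the consent can be given at a later time point, allowing collection of baseline data to be conducted retrospectively", and footnote b of the Cohort 1 schedule says "data will be captured retrospectively from the subject's last visit in the original study up to the moment of enrollment in the current study". The Synopsis and Section 3.1 repeat the rule. None of them sets a maximum interval, and inclusion criterion 1.2 sets no limit on time since the last visit in either arm.

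The gap belongs to the endpoint. Footnote f says "All serious adverse events are to be documented for a total of 60 months after prime vaccination", footnote c counts the 60 months from prime vaccination including the original study, and the first endpoint in Section 11.1 runs over the same window.

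On recording, Section 9.2.2 opens with "For the prospective study period, all serious adverse events, related or not related, following exposure of subjects" and does not mention the gap.

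On analysis, Section 11.5 promises "the number of events per person-year (where applicable) with corresponding 2-sided 95% confidence intervals will be provided, for each cohort and by original randomization". It does not distinguish modes of capture. The Restricted Analysis set in Section 11.3 deals with protocol deviations and enrollment in other studies, not with the gap.

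On placebo, Section 10.2 says "After unblinding of their original study, subjects who received placebo will be withdrawn from further participation". Sections 3.1 and 4 say that unblinding of the ongoing Phase 2 and 3 studies is delayed, without a date, and that placebo subjects are approached before it happens.

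**The concern.** Follow-up of a Cohort 1 subject can have three parts: the original study, copied from its data set; the gap, reconstructed at Visit 1; and the 6-monthly contacts. Section 3.2 justifies the design by the third part: "Prospective data collection facilitates active pharmacovigilance via real-time identification and reporting of serious adverse events". The gap does not work that way, yet the protocol lets it be of any length and places it in the same rate.

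The protocol treats long silence differently once a subject is enrolled. Under Section 9.1, a subject who cannot be reached within 365 days is considered lost to follow-up. A pre-consent silence of the same length or more would count as ordinary follow-up.

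If gap person-time is counted in full but gap events are found less completely, the vaccine SAE rate falls. The shortfall sits in the period after the original study, which is the period this study was set up to describe. The study is descriptive, so the absolute rate is its main product.

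The wording of Section 9.2.2 adds a collection risk. A site that follows it alone could overlook gap SAEs, and no later analysis can recover events that were never collected.

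**Working it through.** The protocol states no gap length, capture probability or SAE rate, so there is no figure of its own to reproduce. Only the 60-month horizon comes from the document. The other inputs are assumptions: O = 12 months in the original study; gap G = 12 or 24 months; capture in the gap relative to 6-monthly contact s = 0.5 to 0.9; a constant true SAE rate; 60 months completed; and gap person-time counted in full.

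**Affected subjects.**

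- 0-60 month rate relative to truth = (O + s·G + (60 − O − G))/60 = 1 − (G/60)(1 − s). O cancels here.
- Rate after the original study relative to truth = (s·G + (60 − O − G))/(60 − O).

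With s = 0.5 and G = 12: (12 + 6 + 36)/60 = 0.90, and (6 + 36)/48 = 0.875.
With s = 0.5 and G = 24: (12 + 12 + 24)/60 = 0.80, and (12 + 24)/48 = 0.75.

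| G (months) | s | 0-60 month rate / truth | Post-original-study rate / truth |
|---|---|---|---|
| 12 | 0.5 | 0.90 | 0.875 |
| 12 | 0.7 | 0.94 | 0.925 |
| 12 | 0.9 | 0.98 | 0.975 |
| 24 | 0.5 | 0.80 | 0.75 |
| 24 | 0.7 | 0.88 | 0.85 |
| 24 | 0.9 | 0.96 | 0.95 |

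**Whole vaccine arm.** With a share f of late enrollees, the factor is 1 − f·(G/60)·(1 − s). At s = 0.5:

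- f = 0.25, G = 12: 1 − 0.25 × 0.2 × 0.5 = 0.975
- f = 0.5, G = 12: 0.95
- f = 0.5, G = 24: 0.90
- f = 1, G = 24: 0.80

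**Active versus placebo.** Placebo follow-up stops at unblinding. Take it as 24 months (assumed), with everyone having the stated gap, s = 0.5 and a true ratio of 1. The placebo factor is 1 − (gap/24) × 0.5.

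| Vaccine gap | Placebo gap | Vaccine factor | Placebo factor | Apparent ratio |
|---|---|---|---|---|
| 24 | 0 | 0.80 | 1.00 | 0.80 |
| 24 | 6 | 0.80 | 0.875 | 0.91 |
| 24 | 12 | 0.80 | 0.75 | 1.07 |
| 12 | 12 | 0.90 | 0.75 | 1.20 |

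An equal gap is a larger share of the shorter placebo follow-up, so the direction can reverse.

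**With the gap removed from both numerator and denominator.** (60 − G)/(60 − G) = 1.00, whatever s is.

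**The case against.** Several parts of the other side's case stand.

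- A reader might infer that only vaccinees can have long gaps, so that the comparison leans toward no harm. The text does not support this. Placebo subjects may also consent late while their study stays blinded, and no unblinding date is given. What is confined to vaccinees is a gap running past unblinding. The table above gives apparent ratios from 0.80 to 1.20.
- A reader might infer that Section 9.2.2 leaves gap SAEs unrecorded. It is silent on the gap. Footnotes b and f and Section 9.1 require capture, and Section 8 covers medication for SAEs over the whole 60 months. The text is narrower than its neighbours and needs aligning, but it is not an instruction to omit.
- A reader might infer that the gap rests on the subject's memory. The protocol does not say so. Section 17.4 requires source documents for all SAEs, and Section 17.8 names hospital and clinic records. Many SAEs leave such records, and Visit 1 is a site visit.
- Scheduled contacts also look back 6 months, preferably by phone, so only gaps well beyond that length differ materially.
- Late consent is the fallback, not the preferred route, and Section 11.2 acknowledges observational bias and missing data in general.
- Section 11 leaves statistical details to the SAP, which is not at hand and may define person-time.
- Dropping gap events from the headline rate would depart from the Section 11.1 endpoint and remove known SAEs from the main estimate of a safety study.

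These points narrow the finding and shape the remedy. They do not supply a limit on the gap or a separation of the two kinds of follow-up, and the SAP cannot settle the recording rule for sites.

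**Conclusion.** The point holds in limited form. The gap is unlimited, lies inside the 60-month endpoint, and is not distinguished from prospectively followed time in Section 11.5. The absolute vaccine SAE rate is biased low whenever gap capture is below that of 6-monthly contact and gap time is counted. At 50% capture the rate in affected subjects is 0.90 (12-month gap) or 0.80 (24-month gap) of truth. At 90% capture it is 0.98 or 0.96. For the whole arm the shortfall is multiplied by the share of late enrollees, which is unknown. If capture is complete there is no bias.

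No direction can be claimed for the active-versus-placebo display. The calculation covers events missed in subjects who do enroll; deaths before consent are a separate matter. The change is worth making because the size cannot be known in advance and the separation is cheap.

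**What to change.** 1. In Section 11.5, keep the 0-60 month rate as the stated endpoint. Split each Cohort 1 subject's events and person-years at the last original-study visit and at the roll-over consent date. Report beside the pooled rate, by arm: (a) the rate and interval with gap events and gap person-time both removed; (b) the gap as its own row, with events, person-years, and median and maximum length.
2. Reconcile Section 9.2.2 with footnotes b and f, so that for Cohort 1 it is clear that SAEs are recorded from the last original-study visit (retrospectively up to consent) and then prospectively.

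Cost: one analysis sentence and one wording alignment. Both dates should already be held. The rate without the gap loses a fraction f·G/60 of the person-time, for example 0.25 × 12/60 = 5% or 0.5 × 24/60 = 20%, so its interval is somewhat wider. No event is lost, because the pooled rate and the gap row keep them all.
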